### Visit 4 Day 85 ± 3 days

- Record adverse events as reported by participant or observed by investigator (visit with provider may take place via telehealth).
- Document any changes in Medical History, Concomitant Medications
- Perform and record physical exam findings (may be limited if performed virtually).
- Document ECOG performance status

- Collect Cycle 4 Day 1 labs: CBC, CMP, SPEP, sFLC, Serum Immunoglobulins (Labs should be drawn 24-48 hours prior to injection date)
- Document Current Multiple Myeloma Disease Status
- Complete the following surveys electronically (Surveys will be completed 3-5 days after the treatment day):
  - Cancer Treatment Satisfaction Survey
  - EORTC QLQ-C30
  - COST Survey
  - OOCAT Survey
- Barriers Assessment
  - Delay in anti-neoplastic therapy, delivery of medication, nurse arrival
  - Any wasted drug
  - Issues with storage or disposal of medication
  - Other issues that arise
- Patient to take Pre-meds prior to nurse arrival
- Administer DARZALEX FASPRO at home. No observation period needed.

### **Visit 5 Day 113 ± 3 days**

- Record adverse events as reported by participant or observed by investigator (visit with provider may take place via telehealth).
- Document any changes in Medical History, Concomitant Medications
- Perform and record physical exam findings (may be limited if performed virtually).
- Document ECOG performance status
- Collect Cycle 5 Day 1 labs: CBC, CMP, SPEP, sFLC, Serum Immunoglobulins (Labs should be drawn 24-48 hours prior to injection date)
- Document Current Multiple Myeloma Disease Status
- Complete the following surveys electronically (Surveys will be completed 3-5 days after the treatment day):
  - Cancer Treatment Satisfaction Survey
  - EORTC QLQ-C30
  - COST Survey
  - OOCAT Survey
- Barriers Assessment

- Delay in anti-neoplastic therapy, delivery of medication, nurse arrival
- Any wasted drug
- Issues with storage or disposal of medication
- Other issues that arise
- Patient to take Pre-meds prior to nurse arrival
- Administer DARZALEX FASPRO at home. No observation period needed.

### **Visit 6 Day 141 ± 3 days**

- Record adverse events as reported by participant or observed by investigator (visit with provider may take place via telehealth).
- Document any changes in Medical History, Concomitant Medications
- Perform and record physical exam findings (may be limited if performed virtually).
- Document ECOG performance status
- Collect Cycle 6 Day 1 labs: CBC, CMP, SPEP, sFLC, Serum Immunoglobulins(Labs should be drawn 24-48 hours prior to injection date)
- Document Current Multiple Myeloma Disease Status
- Complete the following surveys electronically(Surveys will be completed 3-5 days after the treatment day):
  - Cancer Treatment Satisfaction Survey
  - EORTC QLQ-C30
  - COST Survey
  - OOCAT Survey
- Barriers Assessment
  - Delay in anti-neoplastic therapy, delivery of medication, nurse arrival
  - Any wasted drug
  - Issues with storage or disposal of medication
  - Other issues that arise
- Patient to take Pre-meds prior to nurse arrival
- Administer DARZALEX FASPRO at home. No observation period needed.

### **Visit 7 Day 169 ± 3 days**

- Record adverse events as reported by participant or observed by investigator
- Document any changes in Medical History, Concomitant Medications

- Perform and record physical exam findings.
- Document ECOG performance status
- Collect Cycle 7 Day 1 labs: CBC, CMP, SPEP, sFLC, Serum Immunoglobulins
- Document Current Multiple Myeloma Disease Status
- Complete the following surveys electronically (Surveys will be completed 3-5 days after the treatment day):
  - Cancer Treatment Satisfaction Survey
  - EORTC QLQ-C30
  - COST Survey
  - OOCAT Survey
- Administer DARZALEX FASPRO in the infusion center. No observation period needed.

### **Visit 8 Day 197 ± 3 days**

- Record adverse events as reported by participant or observed by investigator.
- Document any changes in Medical History, Concomitant Medications
- Perform and record physical exam findings.
- Document ECOG performance status
- Collect Cycle 8 Day 1 labs: CBC, CMP, SPEP, sFLC, Serum Immunoglobulins, LDH, Uric Acid
- Document Current Multiple Myeloma Disease Status
- Complete the following surveys electronically (Surveys will be completed 3-5 days after the treatment day):
  - Cancer Treatment Satisfaction Survey
  - EORTC QLQ-C30
  - COST Survey
  - OOCAT Survey
- Administer DARZALEX FASPRO in the infusion center. No observation period needed.

### **6.3 End of Treatment Study Procedures**

#### **Final Study Visit (Visit 9, Day 198 + 45 days)**

- Record adverse events as reported by participant or observed by investigator (visit with provider may take place via telehealth).

- Perform and record physical exam findings.
- Document ECOG performance status
- Perform semi-structured qualitative interview with patient to evaluate perceptions of home vs. infusion center based administration of treatment.

## 6.4 Post-treatment/Follow-Up

N/A

## 6.5 Long Term/Survival Follow-up

N/A

# 7 Study Procedures and Evaluations

## 7.1 Study Procedures/Evaluations

- Medical History – Includes documentation of the patient's medical history at time of enrollment and any changes that occur during the duration of the study.
- Medication History – Includes documentation of the patient's medication list at time of enrollment and any changes that occur during the duration of the study. Includes both prescription and over the counter medications.
- The following Questionnaires will be administered either in person and completed on a tablet or remotely through a link that will be distributed via the participants email.
  - Cancer Treatment Satisfaction Survey
  - EORTC QLQ-C30
  - COST Survey
  - OOCAT Survey
- Semi Structures Qualitative Interview will be conducted. Interviews will be conducted by a member of the research team. All interviews will be recorded and transcribed.
- Barrier Assessment of home administration of anti-neoplastic therapy.
  - Delay in anti-neoplastic therapy, delivery of medication, nurse arrival
  - Any wasted drug
  - Issues with storage or disposal of medication

## 7.2 Laboratory Procedures/Evaluations

### 7.2.1 Clinical Laboratory Evaluations

**HBV Serology:** All subjects will be tested locally for hepatitis B surface antigen (HBsAg), hepatitis B surface antibody (Anti-HBs), and hepatitis B core antibody (Anti-HBc) at Screening.

**HBV DNA Tests:** Subjects who are positive for Anti-HBc or Anti-HBs will undergo testing for hepatitis B DNA by PCR. Subjects with serologic findings suggestive of HBV vaccination (Anti-HBs positivity as the only serologic marker) and a known history of prior HBV vaccination do not need to be tested for HBV DNA by PCR. During and following study treatment, subjects who have history of HBV infection will be closely monitored for clinical and laboratory signs of reactivation of HBV as per institutional policy.

All other laboratory studies are per standard of care and per institutional guidelines for management and monitoring of patients with multiple myeloma.

### **7.2.2 Special Assays or Procedures**

N/A

### **7.2.3 Specimen Preparation, Handling, and Storage**

N/A

### **7.2.4 Specimen Shipment**

N/A

## **8 Evaluation of Safety**

### **8.1 Specification of Safety Parameters**

#### **8.1.1 Product Quality Complaints**

A PQC may have an impact on the safety and efficacy of a Company product. Timely, accurate, and complete reporting and analysis of PQC information from studies are crucial for the protection of patients, investigators, and the Company, and are mandated by regulatory agencies worldwide. The Company has established procedures in conformity with regulatory requirements worldwide to ensure appropriate reporting of PQC information. The Institution agrees that Lot and/or Batch #'s shall be collected, when available, for all PQC reports, including reports of failure of expected pharmacological action (i.e., lack of effect) of a Janssen Medicinal Product. A sample of the suspected product shall be maintained for further investigation if requested by the Company.

Any complaint that indicates a potential quality issue during manufacturing, packaging, release testing, stability monitoring, dose preparation, storage or distribution of the product or delivery system is considered a PQC. Not all PQCs involve a patient.

Examples of PQC include but are not limited to:

- Mislabelling or misbranding
- Information concerning microbial contamination, including a suspected transmission of any infectious agent by a product
- Any significant chemical, physical, or other changes that indicate deterioration in the distributed product
- Any foreign matter reported to be in the product
- Mixed product, e.g., two drugs are mixed-up in the packaging process
- Incorrect tablet sequence (e.g., oral contraceptive tablets)
- Insecure closure with serious medical consequences, e.g., cytotoxics, child-resistant containers, potent drugs
- Suspected counterfeit or tampered product
- Adverse Device Effects including any adverse event resulting from insufficiencies or inadequacies in the instructions for use, the deployment, implantation, installation, operation, or any malfunction of a medical device or combination product. This also includes any event that is a result of a use error or intentional misuse and dosing device malfunctions (e.g. auto-injector button not working, needle detaching from syringe, etc.)
- Physical defect (e.g. abnormal product odor, broken or crushed tablets, etc.)

### **8.1.2 Unanticipated Problems**

Unanticipated problems (UAPs) include, in general, any incident, experience, or outcome that meets the following criteria:

- unexpected in terms of nature, severity, or frequency given (a) the research procedures that are described in the protocol-related documents, such as the IRB-approved research protocol and informed consent document; and (b) the characteristics of the participant population being studied;

UAPs are considered to pose risk to participants or others when they suggest that the research places participants or others at a greater risk of harm (including physical, psychological, economic, or social harm) than was previously known or recognized.

### **8.1.3 Adverse Events**

An adverse event is any untoward or unfavorable medical occurrence in a human participant, including any abnormal sign (for example, abnormal physical exam or laboratory finding), symptom, or disease, temporally associated with the participant's participation in the research, whether or not considered related to the participant's participation in the research.

### **8.1.4 Adverse Events of Special Interest**

Adverse events of special interest are events that Janssen Scientific Affairs, LLC is actively monitoring as a result of a previously identified signal (even if non-serious). Adverse events of special interest of daratumumab will be reported to the Company as defined in the protocol. In case of any amendments to the AESI list, Company will notify the Institution/Investigator and the Institution/Investigator will inform sites. Institution/Investigator will ensure that these changes are updated in the protocol as soon as practical.

Adverse events of special interest are events that the COMPANY is actively monitoring as a result of a previously identified signal (even if non-serious).

These adverse events are:

- Infusion reactions: ≥ Grade 3
- Infections: ≥ Grade 4
- Cytopenias: ≥ Grade 4
- HBV Reactivation
- Other malignancies

#### 8.1.5 Serious Adverse Events

A serious adverse event (SAE) is one that meets one or more of the following criteria:

- Results in death
- Is life-threatening (places the participant at immediate risk of death from the event as it occurred)
- Is disabling or incapacitating
- Results in inpatient hospitalization or prolongation of existing hospitalization
- Results in a persistent or significant disability or incapacity
- Results in a congenital anomaly or birth defect
- An important medical event that may not result in death, be life threatening, or require hospitalization may be considered an SAE when, based upon appropriate medical judgment, the event may jeopardize the participant or may require intervention to prevent one of the outcomes listed in this definition.
- Is considered medically significant\*

\*Any untoward medical occurrence that is considered medically significant. Medical and scientific judgment should be exercised in deciding whether expedited reporting is appropriate in other situations, such as important medical events that may not result in death, be life-

threatening or require hospitalization but may be considered a serious adverse drug experience when, based on appropriate medical judgement, that may jeopardize the patient or subject and may require medical or surgical intervention to prevent one of the other outcomes listed in the bulleted list above. Examples of such medical events include allergic bronchospasm requiring intensive treatment in an emergency room or at home, blood dyscrasias or convulsions that do not result in hospitalization, or development of drug dependency or drug abuse or malignancy.

### 8.1.6 Hospitalizations

For reports of hospitalization, it is the sign, symptom or diagnosis which led to hospitalization that is the serious event for which details must be provided. Any event requiring hospitalization or prolongation of hospitalization that occurs during a study must be reported as a serious adverse event, except hospitalizations for the following:

- Hospitalizations not intended to treat an acute illness or adverse event (e.g., social reasons such as pending placement in long-term care facility)
- Surgery or procedure planned before entry into a study. [Note: Hospitalizations that were planned before the signing of ICF and where the underlying condition for which the hospitalization was planned has not worsened will not be considered serious adverse events. Any adverse event that results in a prolongation of the originally planned hospitalization is to be reported as a new serious adverse event.]

### 8.1.7 Life-threatening Conditions

Disease progression should not be recorded as an adverse event or serious adverse event term; instead, signs and symptoms of clinical sequelae resulting from disease progression/lack of efficacy will be reported if they fulfil the serious adverse event definition.

**If no SAE** is associated with the special situation, the special situation should be recorded in the CRF and sent annually to Janssen Scientific Affairs, LLC.

These safety events may not meet the definition of an adverse event; however, the Parties agree that for reporting purposes, they are deemed to be adverse events.

### 8.1.8 Special Situations

The following special situations must be reported to Company with or without an associated serious adverse event (SAE):

- Drug exposure during pregnancy (paternal, maternal)
- Suspected transmission of any infectious agent via administration of a Janssen Product(s) under study.

The following special situations must be reported to the Company when associated with a serious adverse event (SAE):

- Overdose of Janssen Product(s) under study
- Exposure to Janssen Product(s) under study from breastfeeding
- Suspected abuse/misuse of Janssen product(s) under study
- Inadvertent or accidental exposure to Janssen Product(s) under study
- Any failure of expected pharmacological action (i.e., lack of effect) of Janssen Product(s) under study
- Medication error (includes potential, intercepted or actual) involving a Janssen product (with or without patient exposure to the Janssen Product(s) under study, e.g., name confusion)
- Unexpected therapeutic or clinical benefit from use of Janssen Product(s) under study

## 8.2 “Extraordinary” correspondence

Correspondence with a regulatory authority or ethics committee regarding a safety issue that may impact the safety or benefit-risk balance of the Janssen Product(s) Under Study, and/or may impact patients or public health. Examples include:

- Safety issues relating to a quality defect
- Major safety issues identified with changes in the nature, severity or frequency of known serious adverse reactions which are medically significant or the detection of new risk factors for the development of a known adverse reaction or a new serious adverse reaction.
- Major safety issues identified in the context of ongoing or newly completed post-marketing studies e.g. an unexpected increased rate of fatal or life-threatening adverse events.

## 8.3 Safety Assessment and Follow-Up

The PI will follow adverse events with start dates occurring any time after informed consent is obtained until 7 (for non-serious AEs) or 30 days (for SAEs) after the last day of study participation. At each study visit, the investigator (or designee) will inquire about the occurrence of AE/SAEs since the last visit. Events will be followed for outcome information until resolution or stabilization.

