### Visit 9 No later than 45 days After C8D1

Perform Semi-structured  
qualitative interview  
AE Assessment

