#### 8.5.4.1.2 **General**

The Institution / Investigator shall notify Janssen immediately in case of a suspension of recruitment or premature stop of the concerned clinical study because of a safety concern; preferably by means of a telephone contact with the Company Representative, alternatively by email within twenty-four (24) hours of the decision.

Institution / Investigator shall provide to the Janssen copies of any and all relevant extraordinary (not including routine initial or follow-up ICSR submission) correspondences with health authorities and ethics committees regarding any and all serious adverse events (irrespective of the association with the Janssen Product(s) Under Study). Copies of such correspondence shall be provided within 24 hours of such report or correspondence being sent to applicable health authority.

Training: Institution of the Study shall be responsible for training the Study personnel (including the Investigator) on managing safety information arising from the Study according to agreed procedures and the requirements of this Agreement.

Management of Safety Data: The Institution and Investigator will provide safety information arising from the Study to the Company on adverse events, special situations including pregnancies and product quality complaints as defined within this exhibit. This safety information will be documented by the Investigator and reported as described in this exhibit from the time a subject has signed and dated an Informed Consent Form (ICF) until 30 days after the last dose of the Janssen Product(s) Under Study. All subsequent AEs and SAEs beyond 30 days after the last dose of the Janssen Product(s) under study shall be collected/reported if the investigator considers the AE/SAE to be causally related to the use of the Janssen Product(s) Under Study.

For the purposes of this Study, the Janssen Product(s) Under Study is (are):

DARZALEX FASPRO® (daratumumab hyaluronidase-fihj)

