Opportunity cost survey		X	X	X	X	X	X	X	X		
Safety Assessments											
AE assessment	X	X	X	X	X	X	X	X	X		
Schedule of events											
For patients transitioning from IV to Subcutaneous therapy											
Events	Screening	Infusion Center		Home Infusion				Infusion Center		End of Study Assessment	Notes

	Day -30 to 0	C1D1 (+/-3 days)	C2D1 (+/-3 days)	C3D1 (+/-3 days)	C4D1 (+/-3 days)	C5D1 (+/-3 days)	C6D1 (+/-3 days)	C7D1 (+/-3 days)	C8D1 (+/-3 days)	No later than 45 days after last treatment cycle	
Physical Exam (can be virtual exam)	X	X	X	X	X	X	X	X	X	X	
ECOG assessment	X	X	X	X	X	X	X	X	X	X	
Barriers Assessment											
Delay in treatment				X	X	X	X				
Delay in medication delivery to home				X	X	X	X				
Delay in nurse arrival				X	X	X	X				
Wasted drug				X	X	X	X				
Issues with storage/disposal of drug				X	X	X	X				
Other supply chain issues				X	X	X	X				
Patient Interview										X

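### Sections 8.3 and 8.5.4.1.2 set conflicting collection windows for non-serious adverse events, and the Section 8.3 window can close before 30 days after the last dose

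*Combined protocol and SAP*

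**What the plan says.** Two sections of the protocol set the collection window.

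- **Section 8.3** has the principal investigator follow events that start after consent and "until 7 (for non-serious AEs) or 30 days (for SAEs) after the last day of study participation". The protocol does not define that last day. The section also requires an inquiry about adverse events at every study visit.
- **Section 8.5.4.1.2** has the investigator document and report safety information from consent "until 30 days after the last dose of the Janssen Product(s) Under Study". It makes no distinction by seriousness: the next sentence begins "All subsequent AEs and SAEs beyond 30 days after the last dose" and keeps later events in scope only if the investigator judges them causally related.

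The last planned dose is at "Visit 8 Day 197 ± 3 days". The closing visit is headed "Final Study Visit (Visit 9, Day 198 + 45 days"; the schematic and Appendix A likewise give it only a latest date.

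Section 6.3 lists for that visit "Record adverse events as reported by participant or observed by investigator (visit with provider may take place via telehealth", and the schematic lists "AE Assessment". In Appendix A, however, the row "AE assessment" is marked at screening and at the eight cycles but not at End of Study. The physical examination and ECOG rows do carry the End of Study mark.

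Under Section 4.4.2, a participant who withdraws early goes on with treatment at the infusion center as standard of care. That participant is offered an end-of-study visit, which is described as the interview.

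**The concern.** For non-serious events the two rules differ in both length and starting point, and nothing says which governs. A site that works from Section 8.3 can close collection in good faith while Section 8.5.4.1.2 still requires it.

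Safety of home administration is a secondary objective, measured through collected adverse events (Sections 2.1.2 and 2.2.2). If the window depends on when the final visit happens to be booked, participants have unequal follow-up for reasons unrelated to safety. A participant who stops in the home phase may have the least. Section 8.1.4 also lists events of special interest that count even when non-serious. Such an event could fall inside the reporting window of Section 8.5.4.1.2 and outside that of Section 8.3.

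**Working it through.** **Inputs.** Section 8.3: 7 days (non-serious) and 30 days (serious) from the end of participation, P. Section 8.5.4.1.2: 30 days from the last dose, D. Section 6.2: visit days, and surveys due 3 to 5 days after each dose. Section 6.3: final visit from Day 198 to 198 + 45 = Day 243. The schematic counts 45 days from C8D1 instead: 197 + 45 = Day 242.

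**Calendar check.** Dose days 1 + 28k for k = 0 to 7 are 1, 29, 57, 85, 113, 141, 169 and 197. These match Visits 1 to 8, so D = 197 for a completer dosed on the nominal day.

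**Formula.** Section 8.3 closes for non-serious events on P + 7, and Section 8.5.4.1.2 on D + 30. The shortfall is (D + 30) − (P + 7) = 23 − (P − D). It is zero when P − D = 23, which for a completer is Day 197 + 23 = Day 220.

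**Completer.** Section 8.5.4.1.2 closes on 197 + 30 = Day 227.

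| Participation taken to end | P | 8.3 closes | Days after dose | Shortfall against 30 |
|---|---|---|---|---|
| On the dose day | 197 | 204 | 7 | 23 |
| Final visit at its earliest | 198 | 205 | 8 | 22 |
| Cycle 8 survey, 3 days after dose | 200 | 207 | 10 | 20 |
| Cycle 8 survey, 5 days after dose | 202 | 209 | 12 | 18 |
| Break-even | 220 | 227 | 30 | 0 |
| Latest final visit (schematic) | 242 | 249 | 52 | none (22 days longer) |
| Latest final visit (Section 6.3) | 243 | 250 | 53 | none (23 days longer) |

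The survey rows give the realistic minimum for a completer who follows the schedule, because the Cycle 8 survey falls after Day 198. The 8-day row applies only if that survey is missed or is not counted as participation.

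**Leaving in Cycles 3 to 6 on the day of a home dose.**

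| Home dose day | 8.3 closes (+7) | 8.5.4.1.2 closes (+30) | Shortfall |
|---|---|---|---|
| 57 | 64 | 87 | 23 |
| 85 | 92 | 115 | 23 |
| 113 | 120 | 143 | 23 |
| 141 | 148 | 171 | 23 |

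If the participant instead leaves at the next 28-day visit without being dosed, Section 8.3 gives 28 + 7 = 35 days and there is no shortfall.

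**Serious events.** Section 8.3 gives P + 30 − D days after the last dose. Since P is never before the last on-study dose, this is at least 30. For a completer it runs from 30 (P = 197) to 76 (P = 243).

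**Appendix A.** The adverse event row has 9 marks; the physical examination and ECOG rows have 10. The difference is the End of Study cell.

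**The case against.** The best reply is that the two rules can both be met. Section 8.3 sets the investigator's follow-up, Section 8.5.4.1.2 sets what goes to the funder, and nothing in Section 8.3 forbids recording an event 20 days after a dose. The stated 2 months of follow-up (Section 3.4) and 10 months of participation (Study Summary) also suggest a late end of participation, when Section 8.3 is the longer rule. Related events beyond 30 days stay in scope, and Section 11.2 attaches no test or threshold to adverse events.

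Much of this stands, and it limits the point. Events are lost only where a site applies Section 8.3 alone and participation ends within 23 days of the last dose. It does not remove the conflict: the protocol does not state that both rules apply, Section 6.4 marks post-treatment follow-up as not applicable, and the final visit may be held one day after the last dose.

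A reader might infer more than the documents support:

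- *That the Appendix A blank switches off the final adverse event check and so creates the short window.* Section 6.3, the schematic and the every-visit rule in Section 8.3 all require that check. The page before the appendices also says that supplemental documents are not part of the protocol, so the blank arguably cannot override the body.
- *That 7 or 8 days is the usual follow-up.* It is the extreme low end.
- *That home doses in general have truncated follow-up.* The last two planned doses are at the infusion center, and a continuing participant is asked again at the next visit. A home dose is the last on-study dose only after early exit in Cycles 3 to 6, and the full 23-day shortfall needs exit on the dose day itself. Where treatment continues at the center, a dose about 28 days later would fall inside a 30-day window and mix the two settings.
- *That following Section 8.3 always breaches Section 8.5.4.1.2.* From Day 220 onward it does not.

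**Conclusion.** The conflict between Sections 8.3 and 8.5.4.1.2 is real and confined to non-serious events. For a completer dosed on Day 197, the Section 8.3 window can close 18 to 20 days before the 30-day rule if the Cycle 8 survey is the last contact, or 22 days before it if a Day 198 final visit is. At the other end it can run 23 days longer. For a participant who leaves on a home-dose day in Cycles 3 to 6, it can close 23 days early.

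These figures assume nominal dose days, a final visit that may be held at any time from Day 198 to Day 243, and a site that follows Section 8.3 rather than Section 8.5.4.1.2. How many of the 20 participants would be affected cannot be told from the documents.

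The effect is on the completeness and evenness of the safety summary. The primary analysis is untouched. The missing Appendix A mark is a separate inconsistency. The passages should be reconciled because the correction is small and the objective concerned is a stated one.

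**What to change.** - Reconcile Section 8.3 with Section 8.5.4.1.2 so that all adverse events, serious or not, are collected for at least 30 days after the last on-study dose. Section 8.3 can keep its longer period for serious events.
- Define the anchor. Because Section 4.4.2 has leavers continue treatment at the infusion center, specify the last *on-study* dose and say how events after a later off-study dose are classified.
- Apply the same window after early discontinuation where the participant still consents to follow-up. No wording can secure data after consent is withdrawn.
- Add the End of Study mark to the adverse event row of Appendix A.
- If the final visit falls before the window closes, add one brief telephone or telehealth adverse event contact at its end.

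The cost is protocol wording and at most one short contact for some of the 20 participants. Dosing, visit days and the analysis model do not change.
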